**Table 4: Sample Recruitment Monthly Monitoring**

Date				
Total Subjects evaluated				
Subjects randomized				
Men Randomized (month/cumulative)				
Women Randomized (month/cumulative)				
Whites Randomized (month/cumulative)				
Minorities Randomized (month/cumulative)				
Total Randomized Subjects				

Total Goal for Study (to date)				
--------------------------------	--	--	--	--

The PI or Project Manager/Study Coordinator, in accordance with the Institutional Review Board (IRB), will obtain written informed consent for each study subject. Prior to any data collection, we will provide written and oral explanations of the study's purpose, protocol, risks, and benefits. The candidates will have an opportunity to ask questions and then will be asked to sign the form consenting to participate in the study. All advertisements to recruit subjects will be reviewed and approved by the IRB. The study's Steering Committee-(PI, Site PIs and the Co-investigators), as-well as the IRB must agree upon any amendment or revision to the protocol as the trial progresses. One copy of the informed consent form will be given to each subject. One signed copy will be retained in the investigator's study records. At West Virginia University the consent will be scanned into the patient's electronic medical record.

Protection Against Risk - To prevent adverse events this study will follow IRB review and surveillance. The following actions will be taken to protect subjects from risks.

- a) Subjects will be given the National Sleep Foundation "Drowsy Driving Sleep Sheet" to inform them of the risks associated with drowsy driving.
- b) The consent form indicates that subjects should not drive when sleepy. Subjects are informed they should report any falling asleep while driving events to the Project Manager/ Study Coordinator at the time of the monitoring telephone calls during the intervention.
- c) A form called the "Risks of Daytime Sleepiness" will be reviewed with the subject. Questions at the end will be answered to indicate understanding.
- d) After the intervention has been initiated, if a subject report falling asleep while driving, their treatment group will be unblinded and the subject will be withdrawn from the study.
- e) Questionnaires will be completed in the privacy of the subjects' home; they will be instructed to take rest periods as needed if they find completing the questionnaires as burdensome.
- f) Monitoring physical activity with a SenseWear Armband®, having a venipuncture to draw 30cc of blood by trained phlebotomists and responding to questionnaires have only minimal risks to subjects who participate.
- g) Procedures are in place to maintain the security and confidentiality of subject data. All paper-based records will be kept in a secure location that is locked and accessible only to personnel involved in the study. The EncoreAnywhere™, a patient compliance management system, is a HIPPA approved, secure web-based password protected program that contains de-identified adherence data. Multiple levels of password protection (i.e., record, file, directory, server, and computer levels) will ensure data security. All study data will be backed up nightly. The finalized datasets along with documentation and their corresponding syntax files for analysis will be stored on the secure centralized server and written to a CD for off-site archival. No subject identifiers other than the subject's assigned unique study identifier will be contained in any of the data files or in any of the subject files that are stored in locked filing cabinets.
- h) Sham-CPAP circuits will be inventoried and destroyed after use so that none are used inadvertently by persons other than the subjects randomized to that group.

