**Exclusion criteria include:**

- 1.) A1C > 11
- 2.) Gestational or type 1 DM
- 3.) Sleep duration < 4 hrs per day
- 4.) Change in diabetes medications during the previous 3 months
- 5.) Acute medical or surgical conditions or hospitalization  $\leq$  3 months (e.g. angina, stroke, major surgery, major depression or serious psychiatric conditions)
- 6.) Previous diagnosis of another sleep disorder, oxygen or bi-level PAP required
- 7.) O2 sat. < 75% for > 25% of the ApneaLinkPlus sleep study
- 8.) Cardiovascular events noted during overnight titration sleep study,
- 9.) Prior CPAP
- 10.) Persons in household with CPAP
- 11.) History of near-miss or auto accident during last 12 months
- 12.) Employed in safety sensitive job (i.e. truck driver or airline pilot)
- 13.) Non-ambulatory
- 14.) Regular use of hypnotic or alerting (e.g. modafinil) medications
- 15.) Excessive consumption of alcohol.  
Men: > 4 drinks a day and more than 14 drinks per week  
Women: > 3 drinks a day and > 7 drinks per week
- 16.) Claustrophobia to wearing mask
- 17.) Unable to speak, read & write English
- 18.) Pregnancy
19. Request of PCP

Exclusion criteria were determined to maintain subject safety and study integrity.

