Promotion and Assessment of CPAP Adherence. Our goal is for subjects to use their CPAP/sham CPAP all night/every night. We will enhance the procedures for the promotion of adherence that we employed successfully during the pilot/feasibility study. The education was refined from the protocol developed by Dr. [name]; she will be assisting this proposal as a Consultant. We will utilize motivational enhancing problem solving and review and reinforce principles of good sleep hygiene. Subjects will receive education prior to starting CPAP therapy, e.g., that comfort is improved with the use of heated humidification on CPAP machines. All subjects will be shown various masks and permitted to select the most comfortable mask interface. Brochures will be developed in simple language describing the study and stressing the importance of using the treatment every night. CPAP adherence will be encouraged with a phone call to the subjects by a Sleep Educator after the first night of home use. A refinement from the previous study will be that a Sleep Educator will evaluate CPAP/sham-CPAP adherence nightly for the first 2 nights then at least twice weekly with the EncoreAnywhere™ web-based patient compliance system. The Sleep Educator will phone the subjects at least weekly, and intervene to increase adherence.

**Assessment 2.** An assessment will be done after 6-wks of CPAP/sham-CPAP use. Subjects will be mailed the questionnaires, SenseWear Armband® and the Sleep/Activity/Diet Diary to use for 7-days. They will return to the study site with these items and their glucose meter and pedometer. The assessment includes anthropometric measurements and a venipuncture to obtain no more than 30 cc blood for A1C, fructosamine and lipid profile.

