**Table 3: Rationale for Exclusion Criteria**

Exclusion Criteria	Rationale
A1C $\geq$ 11.0%	These individuals may need changes in diabetes medications
Type 1 or gestational DM	Etiology not associated as directly with OSA as T2DM
Sleep duration $<$ 4 hrs per day	Inadequate sleep may be confounding barrier in addition to OSA
Diabetes meds: change in oral medications or $>$ 10% change in insulin in last 3 months	Improvement in diabetes control from med change may confound results
Acute medical or surgical conditions or hospitalization $\leq$ 3 months (such as angina, stroke, major surgery, major depression or serious psychiatric conditions)	Subject may be unstable and inappropriate for clinical trial
Previous Dx. of another sleep disorder	Additional sleep disorders may result in continued sleep disturbance
Oxygen or bi-level PAP required	Unable to randomize to sham-CPAP
O2 sat. $<$ 75% for $>$ 25% of the Dx. PSG	Significant hypoxia presents a danger to delay treatment
Prior CPAP or persons in household with CPAP	Increased difficulty in maintaining blinding to CPAP vs sham-CPAP
Cardiovascular events noted during overnight titration sleep study	Significant cardiovascular events presents a danger to delay treatment
Hx. of near-miss or auto accident during last 12 months	Danger of accident from sleepiness
Employed in safety sensitive job (i.e. truck driver or airline pilot)	Danger of accident from sleepiness
Non-ambulatory	Physical activity with walking is aim of study
Regular use of hypnotic or alerting (e. g. modafinil) medications	May interfere with nighttime sleep or daytime alertness
Consumption of alcohol: Men: <math>></math> 4 drinks a day and more than 14 drinks per week Women: <math>></math> 3 drinks a day and <math>></math> 7 drinks per week	May interfere with nighttime sleep or daytime alertness
Claustrophobia to wearing mask	Potentially unable to wear CPAP mask
Unable to speak, read & write English	Not able to perform study tests and participate in the DEC sessions
Pregnant or intend to become pregnant in the next four months (postmenopausal or confirmed not pregnant by a urine pregnancy test)	Changes in respiration, sleep, and energy potentially confound the results
Primary Care Provider request	Subject may be unstable or otherwise inappropriate for clinical trial

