#### Potential Risks

There are a few potential risks to the proposed protocol. The procedures and standardized tests required by this protocol are all standard assessment techniques that are widely used on patients. The standardized tests employed in the project pose minimal risk to subjects. We will also take precautions to ensure that no patient who is sleepy is permitted to drive home at the end of an assessment visit. Participants will be informed of the danger of driving while sleepy and asked not to drive when experiencing sleepiness. Subjects will be informed that their use of CPAP will be monitored. Except for untreated daytime sleepiness, there are no known risks to the application of the sham-CPAP. As described above, there is no hazard of CO2 retention or exacerbation of nocturnal symptoms including respiratory events. This placebo has been used in previous research without any serious adverse incident (personal interview [name], APPLES PI, May 29, 2008) and data from the CATNAP ([name], Consultant) trial indicates minimal risk to study participants. Subjects will experience side effects associated with the technological interface as they would with active CPAP treatment.

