#### Unmasking (Unblinding) of Treatment

If there is a serious adverse event, anticipated to be an uncommon occurrence, the PI, Medical Directors, Safety Officer or DSMB will, when necessary for the safety of the participant, unmask treatment group assignment. The administration of the intervention may be discontinued at the patient's request or by the investigator, based on clinical judgment. Participants will be instructed to report any adverse event experienced after treatment without delay.

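### Subjects are told to report falling asleep at the wheel at the monitoring calls, so the report that triggers withdrawal may wait for the next call; it should be made at once

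*Combined protocol and SAP*

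**What the plan says.** The rules on driving events during the study are in Section D, in the Protection Against Risk list. Item b says that the consent form warns subjects not to drive when sleepy, and that "they should report any falling asleep while driving events to the Project Manager/ Study Coordinator at the time of the monitoring telephone calls". Item d gives the consequence once the intervention has started: "if a subject report falling asleep while driving, their treatment group will be unblinded and the subject will be withdrawn from the study".

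A general rule stands in the section on unmasking of treatment: "Participants will be instructed to report any adverse event experienced after treatment without delay". The same section adds: "The administration of the intervention may be discontinued at the patient's request or by the investigator, based on clinical judgment". Table 5 requires staff to be notified of each adverse event, and to review it, immediately. The Data and Safety Monitoring Plan provides an independent physician as Safety Officer.

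The only calls described with a weekly interval are in the Procedures section, under promotion of CPAP adherence: "The Sleep Educator will phone the subjects at least weekly, and intervene to increase adherence".

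At entry the plan treats driving events as a hazard. Exclusion 11 is "History of near-miss or auto accident during last 12 months", and Table 3 gives the reason as "Danger of accident from sleepiness". Under Potential Risks the plan states: "Except for untreated daytime sleepiness, there are no known risks to the application of the sham-CPAP".

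**The concern.** Item d is the plan's strongest response to drowsy driving, and only a report sets it off. Item b is the only instruction specific to the event that says when to report, and it points to a scheduled call. A subject who does exactly what item b says may have fallen asleep at the wheel and still be in the blinded study, possibly on sham, until someone rings.

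The risk is one the plan itself names. Apart from side effects of the mask and device interface, untreated daytime sleepiness is the only risk of sham that Potential Risks identifies, and the blinded comparison lasts 12 weeks. The other driving measures are the drowsy-driving handout, the risk form with its questions, the ban on driving home sleepy from an assessment, and the exclusion of safety-sensitive jobs. They educate or screen. None shortens the time between an event and the study's response.

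**Working it through.** No statistical figure in the plan bears on the reporting rule, so the first part of the check sets the texts side by side. Arithmetic enters only for the length of the wait and the price of the fix.

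**1. Which instruction governs?**

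- Item b: specific to falling asleep while driving; timing is the monitoring call; recipient is the Project Manager or Study Coordinator.
- Unmasking section: any adverse event; timing is without delay.
- Item d: acts on any report, whether or not it was made on a call.

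The two timings agree only if the subject regards falling asleep at the wheel as an adverse event. The text supplied does not define the term or place an unharmed episode inside it. With a general rule and a specific one in hand, a subject can reasonably follow the specific one. Item d would accept an earlier report, but item b does not ask for one.

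**2. How long is the wait?**

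Assume that the item b calls are the Sleep Educator's calls and come exactly 7 days apart.

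- Longest wait: 7 days.
- Mean wait, with events spread evenly between calls: 7 / 2 = 3.5 days.

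The calls are to be made at least weekly, so 7 days is the planned maximum. More frequent calls, the two education sessions, the educator's follow-up calls and the 6-week visit could all shorten the wait. If the item b calls are some other calls, the text gives no interval and no maximum can be stated.

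**3. How many events?**

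The documents give no rate of falling asleep at the wheel. No count is estimated.

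**4. What could the fix cost in completers?**

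Inputs from the Sample Size Justification: 210 enrolled, 20% attrition allowance, 84 completers per group, two-sided alpha .01, power .80.

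- Allowance: 210 × 0.20 = 42 losses, or 21 per group.
- Other losses at the 10% cited from the earlier sham-CPAP trial: 210 × 0.10 = 21, which leaves 42 − 21 = 21 in total, or 10.5 per group. The other figure cited, 5%, comes from a 4-week pilot and is likely to be optimistic over 12 weeks.
- Detectable effect, two-sample noncentral t: 84 vs 84 gives d = 0.533, which reproduces the plan's 0.53. If sham ended 5 short, 84 vs 79 gives 0.541. If it ended 10 short, 84 vs 74 gives 0.551.

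The shortfalls of 5 and 10 are illustrative. They show that even a marked loss from sham would move the detectable effect by about 0.02.

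**5. Workload of a backstop question.**

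One question a week for 12 weeks: 12 × 210 = 2,520 askings before attrition, all within calls already planned if the weekly calls are used.

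**The case against.** The strongest reply is that prompt handling is already in the plan. Participants are to report adverse events without delay, Table 5 requires immediate review, adverse events are to be assessed throughout data collection, and item d is not limited to reports made on a call. On this reading item b merely adds a scheduled prompt to a general duty. Subjects also act on the consent form, the handouts and site IRB policy, none of which is in the text supplied, and any of these may already call for immediate reporting. The 7-day figure assumes that two differently described sets of calls are the same. Withdrawal does not itself stop anyone driving, and the warning against driving when sleepy applies throughout.

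Much of this stands. A reader might infer that the plan contradicts itself, or forbids reporting between calls. It does neither: item b does not bar an earlier report, and the general rule may well cover the event. What the reply does not remove is that the one instruction written for this event names a later time than the general rule, and nothing supplied tells the subject which to follow.

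A reader might also infer that crashes and near-misses go unmonitored on study because they are named only at entry. The documents do not support that. A crash or near-miss in which the subject reports having fallen asleep comes under items b and d. An injury crash comes under the adverse event rules. What is left, a drowsy near-miss or non-injury crash without reported sleep, can still reach the Safety Officer or be acted on by the investigator's judgment. An entry exclusion does not oblige the plan to have a matching on-study rule, so naming these events is optional.

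**Conclusion.** The point holds as a mismatch of timing within the safety text. Item b directs subjects to report falling asleep while driving at the monitoring calls, the general rule asks for adverse events without delay, and the text supplied does not settle whether an unharmed episode falls under the general rule. Item d can therefore start late for a subject who follows item b.

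The size is a wait of up to about 7 days, on average 3.5 days with even timing. It rests on the assumption that the calls in item b are the at-least-weekly Sleep Educator calls. The number of subjects affected is unknown. Confidence is medium, because the unseen consent text and handouts could already close the gap; if they do, item b should be brought into line with them. The change is worth making because it corrects a stated rule, bears on safety and costs very little. The attrition and detectable-effect figures price the remedy and are not evidence of a fault in the sample size.

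**What to change.** Reword item b, and the consent text if it says the same, so that subjects in both arms report falling asleep while driving at once to the study contact. Keep the monitoring calls as a backstop with one scripted question, and state which calls these are. Leave item d unchanged.

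Optionally, name any crash or drowsy near-miss in the same sentence, for case-by-case review by the Safety Officer under the existing monitoring and unmasking provisions, without automatic withdrawal.

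The cost is a wording change, IRB approval of it, and one short question per call. The downside is slightly more reports to triage and possibly a few more unblindings and withdrawals under item d, perhaps more in sham, which could make dropout differ between arms. Tabulate these withdrawals by arm for the DSMB so that any imbalance is seen.

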**Assessment 3 with Unblinding/ Debriefing.** (week 12- of CPAP/sham-CPAP use). Subjects will be sent the questionnaires, the SenseWear Armband® to use for 7-days before returning for Assessment #3. Subjects will return to the study site with those items, their glucose meter and pedometer. In addition, they will bring their CPAP/sham-CPAP machines and masks. Anthropometric measurements and a venipuncture to obtain fructosamine, A1C, and lipid profile will be done. Prior to being informed of his/her treatment condition, the subjects will be asked to which arm of the study they think they were assigned. The Project Manager/ Study Coordinator and/or PI will debrief the subject, answer any questions and provide a copy of their sleep and laboratory data.

Crossover to Active CPAP. The crossover to active CPAP is important because of two reasons: 1) ethical considerations and 2) the pilot/feasibility study subjects identified the possibility of eventually being able to try CPAP treatment was a major reason they considered participating in the study. VAPHS subjects who were in either the active and sham-CPAP group will be directed to the Sleep Center at the VAPHS for follow-up care. Non-VAPHS subjects in the sham-CPAP group will be offered the chance to have an actual CPAP titration study, as described above, receive the CPAP education and monitoring, and start CPAP.

**Assessment 4.** (week 24) All subjects are reassessed as described above; it is the final assessment for those who were initially on active CPAP. We will provide those subjects with a summary of their sleep and laboratory data. Those subjects that crossed-over to active CPAP will continue.

**Assessment 5.** (wk 36) Those subjects who crossed-over to active CPAP will have their final assessment (after 24 wks of active CPAP) performed as described above. Subject will receive a final debriefing by the Project Manager /Study Coordinator and/or the PI and a copy of their sleep and laboratory data.

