**Preliminary Analyses.** Detailed exploratory data analyses will first be performed, involving data description and data screening for anomalies (e.g., outliers, nonnormality, etc.). The results from this initial investigation will be used to: 1) describe univariate and bivariate data distributions; 2) identify imbalances between treatment groups and associations between the dependent variables and suspected covariates/confounders); 3) evaluate the amount and patterns of missing data; and 4) check for the violation of statistical assumptions for the planned analyses. Covariates/confounders will be included in models secondarily and their effect on the results of primary predictors/factors will be evaluated. The randomness of missing data will be investigated using available information on subject characteristics to help discern patterns in the missing data, identify the possible covert missing data mechanisms, and inform the choice of the strategies to handle missing data. It is anticipated that the primary reason for data to be missing will be subject attrition. We will closely monitor attrition and conduct logistic regression models via SAS PROC LOGISTIC to compare the characteristics of participants who remained in the study versus those who dropped out to determine if data are missing at random. If the data are missing at random (i.e., not related to the outcome itself), likelihood estimation procedures, such as those used in SAS PROC MIXED, GLIMMIX and NLMIXED as well as Mplus, will produce unbiased estimates while allowing us to retain cases with missing values on the outcome variables. If needed, multiple imputation would be used to impute missing values on the predictor variables. If the data are not ignorably missing, we use pattern mixture or selection modeling to examine data attrition.

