Data Analysis Plan for Primary Aim 1. An "intent-to-treat" (ITT) approach will initially be used during data analysis when investigating efficacy of CPAP+DEC compared to sham-CPAP+DEC. All subjects will be included in the data analysis in the groups to which they were randomly assigned, regardless of the adherence to protocol, treatment received, withdrawal or deviation from protocol. Adherence with the assigned protocol, will be monitored throughout the duration of the study. With this ancillary information, the sensitivity of the results under the ITT model will be explored to identify the effects of the amount of intervention received and the deviations in protocol on the efficacy of the interventions. Since the primary endpoint of interest, glycemic control, is assessed repeatedly using two measures, fructosamine and A1C, linear mixed modeling (LMM) with linear contrasts to test the stated hypotheses. A flexible modeling approach, mixed modeling allows for unequally spaced assessments, fixed and time-varying covariates, dependent variables with data that are missing at random, and modeling the covariance/correlation among longitudinal responses. We will consider the baseline value both as an assessment point as well as a possible covariate in analyses. The primary independent variable is the randomized assignment to treatment (CPAP+DEC vs. sham-CPAP+DEC). Fixed and/or time-dependent covariates (including baseline outcome values) may be included in the repeated measures model as indicated secondarily based on the results on the preliminary data analysis to adjust for group imbalances or variables related to the dependent variable. Prior to fitting the repeated measures model, the structure of the estimated covariance matrix for the repeated measures will be carefully examined to determine the appropriate covariance structure. Fit indices will also be used to evaluate the repeated measures models estimated assuming different covariance structures to identify the most appropriate covariance structure. When fitting models, time will be treated as a fixed, repeated within-subjects factor, while treatment assignment will be a fixed, between-subjects factor, with an interaction between time and group. F-tests will be used to test the main and interaction effects included in the model. Individual regression parameters will be computed and reported with their asymptotic standard errors to yield confidence intervals. Sensitivity analyses will be performed to discern the impact of influential cases on results. To test the associated hypothesis (H1), linear contrasts will be specified and estimated when fitting the repeated measures model to compare, relative to baseline values, the CPAP+DEC and sham-CPAP+DEC groups on: 1) the 6-week values of fructosamine and A1C and the 2) 12-week values of fructosamine and A1C. Wald t-statistics will be used to test each linear contrast. Confidence intervals will be obtained for these linear contrasts. Marginal modeling with generalized estimating equations will also be used as it tends to be more robust to misspecification of the covariance structure of repeated assessments and violations in the normality assumption for continuous outcomes.

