
Analysis Strategy for Aim 2. Using the approach described for Aim 1, repeated measures models will be fitted, and linear contrasts will be estimated to compare 6-week and 12-week values for improvements in diabetes self-management outcomes (retention of information taught during the DEC classes [DKT], improved self-management behaviors [SDSCA], increased physical activity [SenseWare Armband steps], and decreased diabetes-related distress [PAID]) relative to baseline values between subjects on CPAP+DEC and those receiving sham-CPAP+DEC. Generalized linear mixed modeling or nonlinear mixed modeling will be used to analyze longitudinal categorical outcomes should outcome variables need to be categorized for analysis. Along with test statistics and p-values, point and interval estimates will be obtained for linear contrasts.

Analysis Strategy for Aim 3. We will *explore* adherence to CPAP (dose) and specific neuro-behavioral and physiological mechanisms (nighttime sleep, daytime sleepiness, mood, and vigilance during DEC sessions) as possible intervening, or mediator, variables that may mediate the effects of CPAP treatment on glycemic control and diabetes self-management outcomes. Initially, we will fit simple mediational models (predictor, single mediator, single outcome) and estimate whether the effects of CPAP (predictor) on changes in glycemic control and diabetes self-management outcomes are mediated through changes in specific neuro-behavioral and physiological variables (i.e., nighttime sleep, daytime sleepiness, mood, and vigilance during DEC sessions). Standardized parameter estimates of path linkages (with confidence intervals) will be obtained to summarize associations between the exogenous treatment variables, suspected mediators, and distal outcomes, as well as the indirect effect of the treatment group on the targeted outcomes through the suspected mediators and the direct effect of the treatment group on the outcomes. The goodness-of-fit of a model will be assessed using standard summary indices (e.g., RMSEA, CFI) as well as through residual analyses. Depending on the results for testing of individual mediators, we may combine the mediators into a multiple mediator model to develop a more complete picture of these hypothesized mechanisms of action for CPAP.

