**Sample Size Justification.** The study sample size of 210 was determined focusing on the testing of hypotheses associated with the primary aims (Hypotheses 1 and 2) and considering the results of the pilot/feasibility study (reported in Approach), the adjustment of the testwise significance level to .01 to limit inflation of type 1 error due the multiple testing of hypotheses at 6- and 12-weeks follow-up for several outcomes, and the anticipated subject attrition during the 12-weeks of follow-up. Regarding Aim 1, our pilot/feasibility study suggests that CPAP improves glycemic control as measured by serum fructosamine (see Table 1). Therefore, we anticipate large effects (in terms of standardized mean differences,  $d$ ) on the order of  $d = -0.74$  may be detected with 0.80 power with a group sample size of 48 (96 total) when comparing mean changes from baseline to 6 weeks and to 12 weeks in serum fructosamine between CPAP+DEC and sham-CPAP+DEC groups using linear contrasts from a repeated measures model at testwise two-tailed level of significance of .01. Regarding Aim 2, we have observed effect sizes with magnitudes ranging from 0.22 to 1.27 (median effect size of 0.75) for 4-week changes from baseline in physical activity, sleep, vigor, fatigue and vigilance measures (see Table 1). Groups of 84 participants (168 total) will be of sufficient size to detect effect sizes as small as  $d = 0.53$  in mean changes from baseline to 6 weeks and to 12 weeks (based on linear contrasts from a repeated measures model) with 0.80 power at testwise two-tailed level of significance of .01. Although efforts will be made to retain study subjects, some subject attrition is possible. Our recent pilot/feasibility study of active-CPAP with a 4-week follow-up in adults with type 2 diabetes demonstrated low attrition of 5%. In the CATNAP study ([name] et al.) about 10% attrition was observed. To ensure an adequate number of subjects complete the study by conservatively adjusting sample size for 20% attrition, we plan to enroll 210 subjects (105 per group) to have at least 168 subjects (84 per group) complete the study.

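### Subjects who report falling asleep while driving are withdrawn from the whole study, and no visible text provides for collecting their remaining 6- and 12-week outcomes

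*Combined protocol and SAP*

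**What the plan says.** Item d of Protection Against Risk (section D) is mandatory: "if a subject report falling asleep while driving, their treatment group will be unblinded and the subject will be withdrawn from the study".

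The blinded outcomes come from two visits. For Assessment 2, "An assessment will be done after 6-wks of CPAP/sham-CPAP use"; Assessment 3 is placed at "week 12- of CPAP/sham-CPAP use". Neither entry says what happens for a subject who has left under item d. The compensation text pays excluded participants for what they complete, but schedules nothing further.

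On analysis, the Aim 1 plan includes every subject in the randomised group "regardless of the adherence to protocol, treatment received, withdrawal or deviation from protocol". Preliminary Analyses relies on likelihood methods if data are missing at random, and otherwise: "If the data are not ignorably missing, we use pattern mixture or selection modeling to examine data attrition".

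The Aim 3 strategy lists daytime sleepiness, among other measures, "as possible intervening, or mediator, variables that may mediate the effects of CPAP treatment on glycemic control". Potential Risks names untreated daytime sleepiness as the only known risk of sham.

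**The concern.** The Aim 1 text commits to an intention-to-treat comparison that keeps withdrawn subjects. Item d creates withdrawals by rule and leaves their later outcomes uncollected. An event before week 6 costs both follow-up values, so the model has only a baseline for that subject. A later event costs the 12-week value.

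This differs from ordinary attrition because the trigger is tied to the question under study. If active CPAP reduces sleepiness and sham does not, the rule may remove more sham subjects than active ones, and those removed may be the ones doing worse. The documents state no such imbalance and give no rate; it is a plausible mechanism only.

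At stake is whether the intention-to-treat contrast for these subjects rests on measurements or on a missing-data assumption that the trial cannot test.

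**Working it through.** **1. The plan's own figure.** Sample Size Justification states: "Groups of 84 participants (168 total) will be of sufficient size to detect effect sizes as small as" d = 0.53, with 0.80 power at two-sided .01. The normal formula gives n = 2 × (2.576 + 0.842)² / 0.53² = 83.2, so 84 per group. The two-sample t-test (noncentral t) with 84 per group gives power 0.795 for d = 0.53 and 0.985 for the Aim 1 fructosamine effect of 0.74. Enrolment is 168 / 0.80 = 210. The stated size reproduces, and item d does not make it wrong.

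**2. Bias as written.** Inputs from the plan: 84 per group, two-sided .01, d = 0.53 and 0.74. Assumed, because the documents give neither: the proportions withdrawn under item d (p_sham, p_active), and δ, the amount in SD by which withdrawn subjects' 12-week change is worse than that of the others. δ is taken as equal in both arms and uncorrected by earlier data.

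If the remaining subjects in an arm have mean m, the full arm has mean (1 − p)m + p(m − δ) = m − pδ, while the analysis estimates m. The contrast therefore shrinks by (p_sham − p_active) × δ. Power is recomputed at d minus that bias.

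| Assumed sham / active | Bias, δ = 0.5 to 1.0 SD | Aim 2 power (0.795 without bias) | Aim 1 power (0.985 without bias) |
|---|---|---|---|
| 2% / 1% | 0.005 to 0.010 | 0.786 to 0.776 | 0.984 to 0.983 |
| 5% / 2% | 0.015 to 0.030 | 0.767 to 0.736 | 0.981 to 0.976 |
| 5% / 5% | 0 | 0.795 | 0.985 |

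If earlier data correct half the gap at 5% / 2%, the bias is 0.0075 to 0.015 SD and Aim 2 power is 0.781 to 0.767. If the rates ran the other way (2% sham, 5% active), the bias would favour CPAP by 0.015 to 0.030 SD, and per-test type I error would be 0.0103 to 0.0114 instead of 0.010.

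**3. Does follow-up after stopping restore power?** The fix stops the device in both arms. In the worst case, every stopped sham subject starts CPAP and gains 0.53 SD, and every stopped active subject loses 0.53 SD. Then d = 0.53 × (1 − p_sham − p_active):

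- 5% / 2%: 0.53 × 0.93 = 0.493, power 0.721, against 0.767 to 0.736 as written.
- 2% / 1%: 0.53 × 0.97 = 0.514, power 0.765, against 0.786 to 0.776 as written.

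Partial switching would cost less. The fix cannot be justified on power.

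**The case against.** The strongest case for leaving the rule alone has four parts.

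- **Safety.** Ending participation after a subject falls asleep at the wheel is a legitimate, conservative choice. That stands for unblinding and stopping the device. It is weaker for the assessments: the protocol itself treats blood draws and questionnaires as minimal risk, and questionnaires are done at home. Travel is the real hazard.
- **Few events.** Eligibility excludes "History of near-miss or auto accident during last 12 months" and safety-sensitive jobs, and items a to c add drowsy-driving education. The 20% attrition allowance compares with 5% in the pilot and about 10% in an earlier CPAP trial, so it can absorb a few losses. This stands, and keeps the point minor.
- **The analysis already handles it.** Inclusion regardless of withdrawal, likelihood methods, and pattern-mixture or selection models are all planned. They deal with missing values; they do not collect them. Comparing dropouts with completers cannot show that missingness is unrelated to unseen outcomes.
- **Removed pages.** Consent text may address follow-up after withdrawal. It could not be checked, so the point is limited to the visible text.

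Two stronger readings are tempting. A reader might infer from the Unmasking section, which speaks of discontinuing the intervention, that other discontinued subjects are followed while these are not. That section gives no follow-up rule either. A reader might also infer that Assessments 2 and 3 are conditional on continued device use. Their wording sets timing and does not state such a condition.

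**Conclusion.** The point holds in a limited form and is worth considering. Item d, followed as written, loses endpoint values on a sleepiness-linked trigger, and the intention-to-treat comparison must then supply them by assumption. Under assumed rates from 2% / 1% to 5% / 2% and δ of 0.5 to 1.0 SD, the bias is about 0.005 to 0.03 SD. It is zero if the rates and δ are equal across arms. Aim 1 is little affected.

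A reader might infer that the rule threatens a false claim of superiority. The documents do not support that: if sham subjects are withdrawn more often and do worse, the bias is toward the null, and even the reversed rates of 2% and 5% barely move the type I error. Nor do they support a claim that the trial is underpowered because of this rule. All rates and δ are assumptions, so the direction and size are illustrative.

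**What to change.** Reword item d so that the subject is unblinded and the assigned device stopped, but, unless consent is withdrawn, whichever of Assessments 2 and 3 remain are obtained on their original dates and analysed in the randomised arm. At minimum, collect A1C, fructosamine where the site measures it, and the home questionnaires. Require that the subject does not drive to or from the visit, flag data collected after unblinding, and record the date of any early start of active CPAP.

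The cost is protocol and consent wording with IRB approval; the visits are already scheduled. There are three downsides:

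- Self-report is open-label for these few subjects, which matters most for the Aim 2 questionnaires.
- The contrast is diluted if stopped subjects switch treatment.
- Transport may need arranging at West Virginia University, since bus access is stated only for the UPMC and VAPHS sites.

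Outcomes not taken at weeks 6 and 12 cannot be recovered later, which is the reason to make the change despite the small expected effect.
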